1 DEFINITIONS AND ABBREVIATIONS

Term	Description
ADE	Adverse Device Effect
AE	Adverse Event
CBAS	Cochlear Bone Anchored Solutions AB
CER	Clinical Evaluation Report
CHL	Conductive Hearing Loss
CIP	Clinical Investigation Plan
CRF	Case Report Form
DD	Device Deficiency
EC	Ethics Committee
eCRF	Electronic Case Report Form
EDC	Electronic Data Capture
GCP	Good Clinical Practices
IB	Investigator's Brochure
ICF	Informed Consent Form
IFU	Instructions for Use
IMD	Investigational Medical Device
MHL	Mixed Hearing Loss
PI	Principal Investigator
SADE	Serious Adverse Device Effect
SAE	Serious Adverse Event
SAP	Statistical Analysis Plan
SNR	Signal-to-noise Ratio
SOP	Standard Operating Procedure
SP	Sound Processor
SPL	Sound Pressure Level
SSD	Single-sided Sensorineural Deafness
UADE	Unanticipated Adverse Device Effect
USADE	Unanticipated Serious Adverse Device Effect

2 CLINICAL INVESTIGATION SYNOPSIS

Investigation title	A pivotal, prospective, single-centre, randomized test order, crossover, open label study comparing the performance of a new sound processor - Baha 6 Max with unaided hearing and Baha 5 in adult subjects with conductive or mixed hearing loss.
Short title	Baha 6 Max Home test
Investigation number	CBAS5779
Name of investigational medical device(s)	The Baha 6 Max SP
Intended use of investigational medical device(s)	
Intended use
 
The Cochlear Baha System uses bone conduction to transmit sounds to the cochlea (inner ear) with the purpose of improving hearing. The Baha 6 Max SP is intended to be used as part of the Cochlear Baha System to pick up surrounding sound and transfer it to the skull bone via a Baha Implant, Baha Softband or Baha SoundArc and can be used unilaterally or bilaterally.
 
Medical indications for use
 
The Baha System is indicated for patients with conductive hearing loss, mixed hearing loss and single sided sensorineural deafness (SSD). The Baha 6 Max SP is indicated for patients with up to 55 dB SNHL.
 
The regulatory status is pre-market.

Name and description of comparator device/product(s)	
The comparator will be the Baha 5 SP.
 
Intended use
 
The Cochlear Baha System uses bone conduction to transmit sounds to the cochlea (inner ear) with the purpose of improving hearing. The Baha 5 SP is intended to be used as part of the Cochlear Baha System to pick up surrounding sound and transfer it to the skull bone via a Baha Implant, Baha Softband or Baha SoundArc and can be used unilaterally or bilaterally.

	
Medical indications for use
 
The Baha System is indicated for patients with conductive hearing loss, mixed hearing loss and single sided sensorineural deafness (SSD). The Baha 5 SP is indicated for patients with up to 45dB SNHL.
 
The Baha 5 SP is a CE marked medical device.

Expected start date (first subject consented)	The start of the study has been delayed due to Covid-19 pandemic. New estimated start date beginning of September 2020.
Expected enrolment period	6 weeks
Expected duration per subject	14 days +/- 4 days
Expected total duration of the clinical investigation	8 weeks
Number of subjects planned	16
Number of investigational sites planned	One site
Inclusion criteria	
 • Adult subject (18-<70 years of age) • At least 12 months experience from using a Baha Connect system (percutaneous Baha) • Subject with a conductive or mild to moderate mixed hearing loss. that would benefit from improved hearing from bone conduction device as judged by the research audiologist • Willing and able to provide written informed consent
Exclusion criteria	
 • Signs of infection around the implant site • Unable to follow investigational procedures • Unable or unwilling to comply with the requirements of the clinical investigation as determined by the Investigator

	
 Investigator site personnel directly affiliated with this investigation and/or their immediate families; immediate family is defined as a spouse, parent, child, or sibling. Cochlear employees Currently participating, or participated within the last 30 days, in another interventional clinical investigation/trial involving an investigational drug or device.
--	---

Objectives and Endpoints	
Primary Objectives	Primary Endpoints
To compare hearing performance of speech in noise between Baha 6 Max and the unaided hearing (superiority).	Adaptive speech in noise [signal-to-noise ratio, 50% speech understanding]
To compare the preference of device between Baha 6 Max SP and Baha 5 SP	Preference of device
Secondary Objective	Secondary Endpoint
To compare hearing performance between Baha 6 Max and Baha 5 SP in a home/normal hearing environment	
 Diary 
 Daily use of the SP (hours) Change of battery Switch to their own SP and reason for change
To compare hearing performance between Baha 6 Max and Baha 5 SP.	
 Adaptive speech in noise [signal-to-noise ratio, 50% speech understanding] Thresholds audiology, sound-field [0.25, 0.5, 1.0, 2.0, 3.0, 4.0, 6.0, 8.0, 9.0 and 10.0 kHz] Speech in quiet [% correctly perceived words at 65dB SPL] Evaluation of sound quality and listening effort through sound clips
To compare hearing performance between Baha 6 Max and unaided.	
 Thresholds audiology, sound-field [0.25, 0.5, 1.0, 2.0, 3.0, 4.0, 6.0, 8.0, 9.0 and 10.0 kHz] Speech in quiet [% correctly perceived words at 65dB SPL]

Safety Objective	Safety Outcome measures
Adverse events	Information will be collected from Visit 1 and onwards.
Device deficiency	Information will be collected from Visit 1 and onwards.

3 SCHEDULE OF EVENTS

Visit/Type of visit	Visit 1	Visit 2	Visit 3	Extra Visit
Timing of Investigation	Day 0	Day 7	Day 14	
Visit window (±)	± 0 Day	± 2 days	± 2 days	
Baseline information				
Written informed consent	X			
Demographics	X			
Eligibility	X			
Hearing history incl. audiogram	X			
Device history	X			
Medical history	X			
Fitting of SP to be tested		First randomised device to bring home	Second randomised device to bring home	Re-fitting
Feedback test	X	X	X ^a	X ^b
BC-Direct	X	X	X ^a	X ^b
Fine tuning	X ^b	X ^b	X ^b	X ^b
Choice of snap coupling	X ^c	X ^c		X ^c
Test procedures in sound booth		Aided First device	Aided Second device	Unaided
Blocking incl. verification of contralateral ear	X	X	X	
Adaptive speech in noise (Matrix)	X	X	X	
Threshold audiometry in sound-field	X	X	X	
Speech in quiet at 65 dB SPL	X	X	X	
Subjective evaluation by research subject based on home test			First device	Second device
Hand-out Diary	X ^d	X ^d		
Review Diary		X	X	
Preference of device			X	
Subjective evaluation by research subject based on sound clips (blinded evaluation)				First and second device
Evaluation of sound quality and listening effort through sound clips			X ^e	
Safety evaluation				
Adverse Events (AEs)	X	X	X	
Device Deficiencies (DDs)	X	X	X	

^a Reprogram the first randomised device (Baha 5 SP or Baha 6 Max)

^b Should be performed, if needed

^c Only applicable to Baha 6 Max.

^d Instruction on how to complete Diary

^e Randomised order

4 BACKGROUND INFORMATION AND RATIONALE

4.1 Introduction

Developed in the late 1970's, Bone Conduction hearing implant systems are a well-established treatment modality that has proven to be a safe and effective way of providing hearing in patients with Conductive hearing loss (CHL), Mixed Hearing Loss (MHL) or Single-sided Sensorineural Deafness (SSD).

The Cochlear Baha System uses bone conduction to transmit sounds to the cochlea (inner ear) with the purpose of improving hearing.

The Baha Connect system (figure 1) consists of a titanium implant, which connects to a SP (SP) via a skin-penetrating (percutaneous) abutment. The SP (1) transforms sound into vibrations that are transmitted via the abutment (2) and osseointegrated titanium fixture (3) to the skull bone and onwards to the cochlea.

[figure not shown]

Figure 1. Schematic presentation of the Baha Connect System

The new SP - the Baha 6 Max - is intended to be used as part of the Cochlear Baha System to pick up surrounding sound and transfer it to the skull bone via a Baha Implant, Baha Softband or Baha SoundArc and can be used unilaterally or bilaterally. The Baha 6 Max SP is indicated for patients with up to 55 dB SNHL (2).

4.2 Findings of Previous Nonclinical and Clinical Studies

4.2.1 Nonclinical Data

Results from technical verification and validation activities are described in the Investigator's Brochure (3).

4.2.2 Clinical Data

The previously released and comparator device Baha 5 SP has similar characteristics as Baha 6 Max SP (3). The clinical data for Baha 5 SP appraised and analysed from systematic literature review and exploratory clinical investigations demonstrate good objective hearing outcomes, with consistently improved sound-field thresholds (PTA4, mean of 0.5, 1, 2 and 4 kHz), speech recognition in quiet and in noise as compared to the unaided condition. There are no high risks relating to the use of the Baha SPs or accessories (section 3 in IB, (3)).

5 MEDICAL DEVICE INFORMATION

5.1 Identity and Description of the Investigational Medical Device (IMD)

The Baha 6 Max SP is a fully programmable, head-worn, SP with support for direct audio, data streaming and wireless connection to Cochlear Wireless Accessories, among other features. It has been developed to meet the needs of patients with CHL, MHL or SSD (3).

Figure 2. The Baha 6 Max SP

The Baha 6 Max SP receives sound from its two microphones. Digital audio can be received through wireless streaming from the wireless accessories or from a compatible iPhone.

The SP processes the received information and generates a mechanical signal, i.e. a force output that is transferred to the skull of the patient via the implant system. The vibration is generated by an electromagnetic actuator (3).

The SP contains signal processing features to enhance the patient's hearing experience. These are further described in the IB (section 1.2, (3)).

The material used in the Baha 6 Max SP is described in the Investigator Brochure (section 1.2, table 2, (3)).

Research subject that will participate in the investigation are experienced SP users. They will be provided with an Instructions for Use (IFU) (4).

The manufacturer of Baha 6 Max SP is CBAS.

5.2 Identity and Description of the Comparator

The Cochlear Baha 5 SP is the predecessor to Baha 6 Max SP.

The Baha 5 SP uses bone conduction to transmit sounds to the cochlea (inner ear). It is indicated for people with conductive hearing loss, mixed hearing loss and single sided sensorineural deafness (SSD). Furthermore, it is indicated for bilateral and paediatric recipients. Fitting range up to 45 dB SNHL (2).

Baha 5 SP is CE-marked.

Figure 3. The Baha 5 SP

The manufacturer of Baha 5 SP is CBAS.

5.3 Interfaces

An audiologist uses programming software—Fitting Software—to modify hearing profiles in order to provide comfortable and usable gain for the sound processor for each user (Baha Connect System recipient). Communication between the computer-based software and the sound processor is achieved using a Noahlink Wireless programming unit. Baha Fitting Software is used in clinic by audiologists or similar trained hearing healthcare professionals e.g. research audiologists (section 1.3 in IB, (3)).

6 OBJECTIVES AND ENDPOINTS

Primary Objectives	Primary Endpoints

To compare hearing performance of speech in noise between Baha 6 Max SP and the unaided hearing (superiority).
 
To compare the preference of device between Baha 6 Max SP and Baha 5 SP
	
Adaptive speech in noise [signal-to-noise ratio, 50% speech understanding]
 
Preference of device

Secondary Objectives	Secondary Endpoints

To compare hearing performance between Baha 6 Max SP and Baha 5 SP in a home/normal environment hearing environment
	
 • Diary 
 ◦ Daily use of the SP (hours) ◦ Change of battery ◦ Switch to their own SP and reason for change

To compare hearing performance between Baha 6 Max SP and Baha 5 SP.
	
 • Adaptive speech in noise [signal-to-noise ratio, 50% speech understanding] • Thresholds audiology, sound-field [0.25, 0.5, 1.0, 2.0, 3.0, 4.0, 6.0, 8.0, 9.0 and 10.0 kHz] • Speech in quiet [% correctly perceived words at 65dB SPL] • Evaluation of sound quality and listening effort through sound clips

To compare hearing performance between Baha 6 Max SP and unaided.
	
 • Thresholds audiology, sound-field [0.25, 0.5, 1.0, 2.0, 3.0, 4.0, 6.0 and 8.0 kHz] • Speech in quiet [% correctly perceived words at 65dB SPL]
Safety Objective	Safety Outcome measures
Adverse events (AEs)	Information will be collected from Visit 1 and onwards.
Device deficiency (DDs)	Information will be collected from Visit 1 and onwards.

7 DESIGN OF THE CLINICAL INVESTIGATION

7.1 General

[figure not shown]

Figure 4. Schematic for the investigation

This investigation is a pivotal, prospective, single-centre, randomized test order, cross-over, open label investigation comparing the performance of a new SP - Baha 6 Max SP with unaided hearing and Baha 5 SP in adult subjects with conductive or mixed hearing loss.

The evaluation of sound quality and listening effort through sound clips at visit 3 will be performed single-blinded, i.e. the test subject will not know if Baha 6 Max SP or Baha 5 SP is connected to the abutment.

The subjects include men and women aged 18 or older who are currently using the Baha Connect System (percutaneous Baha). Subjects will be screened, and 16 eligible subjects will be enrolled in the clinical investigation. Eligible subjects will be randomly assigned to one of two investigational arms using a 1:1 randomisation ratio. Subjects will be randomised either to first test the Baha 6 Max SP and thereafter Baha 5 SP or Baha 5 SP followed by Baha 6 Max SP.

After signing the informed consent, subjects will attend scheduled study visits over a three-week period to be assessed as described in the CIP Schedule of Events (Section 3). At study visits, subjects will undergo hearing assessments and safety assessments.

The first primary endpoint is to determine the hearing performance of Baha 6 Max SP in comparison with unaided hearing and the second primary endpoint is the comparison of preference between the devices. The second primary objective is to compare the hearing performance between Baha 6 Max SP and Baha 5 SP when it comes to subject preference.

Safety will be assessed by recording and summarising all AEs/ADEs and DDs. All subjects will attend an End-of-Study visit at the time they complete the investigation.

No data monitoring committee will be used for this clinical investigation.

After the investigation a subject will continue to use the SP currently prescribed to him/her.

7.1.1 Design Rationale

The primary purpose with this investigation is to test the Baha 6 Max SP versus unaided hearing in order to achieve regulatory approval and to investigate which device (Baha 6 Max versus Baha 5) the subjects prefer.

The second primary objective is to compare hearing performance between Baha 6 Max SP and Baha 5 SP in a home (normal) hearing environment. The subjects will test the two SPs during a week at home in a cross-over design (randomised test order). Based on their experiences with the SPs the subject will be asked which of them they prefer. Because all subjects are prescribed and used to amplified sound through bone conduction, one weeks testing at home is regarded as sufficient time to evaluate the performance of a SP. The investigation must be performed in an open fashion since it is not possible to blind the investigation due to differences in design.

After fitting of the test device several listening tests (adaptive speech in noise, thresholds audiometry and speech in quiet) will be performed in a sound booth.

The evaluation of sound quality and listening effort through sound clips (visit 3) will be performed in a blinded fashion, i.e. the subject will not know which SP that is tested. The test order will be randomised

7.2 Subjects

Written, informed consent must be obtained from the subject before any study procedures are initiated.

7.2.1 Inclusion Criteria

Subjects must meet all the inclusion criteria described below to be eligible for this clinical investigation.

1. Adult subject (18-<70 years of age)
2. At least 12 months experience from using a Baha Connect system (percutaneous Baha)
3. Subject with a conductive or mild to moderate mixed hearing loss. that would benefit from improved hearing from bone conduction devise as judged by the research audiologist
4. Willing and able to provide written informed consent

7.2.2 Exclusion Criteria

Subjects who meet any of the exclusion criteria described below will not be eligible for this clinical investigation.

1. Signs of infection around the implant site
2. Unable to follow investigational procedures
3. Unable or unwilling to comply with the requirements of the clinical investigation as determined by the Investigator
4. Investigator site personnel directly affiliated with this investigation and/or their immediate families; immediate family is defined as a spouse, parent, child, or sibling.

5. Cochlear employees
6. Currently participating, or participated within the last 30 days, in another interventional clinical investigation/trial involving an investigational drug or device.

7.2.3 Number of Subjects Required

In order to meet the sample sizes calculations for both primary analyses, 16 subjects will be included.

As this is an internal Cochlear investigation, patients will be recruited until the number of required patients are enrolled. Hence, no dropouts are expected.

7.2.4 Vulnerable Populations

No applicable

7.2.5 Enrolment & Study Duration

The following subject status definitions apply:

Screened: A consented subject who is being assessed for eligibility according to the Screening requirements.

Screen Fail: A consented subject that has been determined to not meet all eligibility criteria for enrolment.

Enrolled: First use of the IMD or comparator following completion of screening activities and confirmation of eligibility

The expected duration of each subject's participation in the clinical investigation is 3 weeks, from the time of informed consent to the End of Study visit.

The enrolment period for the clinical investigation is anticipated to be 6 weeks from the time of first subject consent to enrolment of the last subject.

The anticipated total duration of the clinical investigation is therefore 8-9 weeks.

Clinical Investigation completion is last subject last visit. In the event of an ongoing SAEs/SADEs at the time of this last visit, the clinical investigation completion will be extended for a further 30 days, or until resolution or stabilisation of the event, whichever comes first.

7.2.6 Criteria for Subject Withdrawal

Subjects can decide to withdraw from the investigation at any time. The Investigator shall ask the reason(s). The reason for withdrawal should be documented in the subject's source files and the case report form (CRF).

The Investigator or Sponsor may also decide to withdraw a subject from the clinical investigation if it is considered to be in their best interests.

Subject withdrawal may be for any of the following reasons:

- Adverse Event (AE)
- Device Deficiency (DD)

- CIP or GCP deviation
- Subject lost to follow-up
- Subject withdrew consent
- Subject death
- Sponsor decision
- Investigator decision
- Other (specify)

If subject withdrawal is due to problems related to the IMD or comparator safety or performance, the Investigator shall ask for the subject's permission to continue in safety follow up (i.e., adverse events) until their scheduled End-of-Study visit.

If a subject is lost to follow-up, every possible effort must be made by the study site personnel to contact the subject and determine the reason for discontinuation. At least 3 separate attempts taken to contact the subject must be documented.

Enrolled subjects who are withdrawn/discontinued will not be replaced. Randomisation Procedures

The test order between the two SPs will be randomised based on a computer-generated randomisation schedule prepared by the Sponsor.

7.2.6.1 Blinding Procedures

Blinding of the SPs during the home test is not possible due to the differences in design.

When performing the subjective evaluation of sound clips the subjects will be blinded to which SP (Baha 6 Max SP or Baha 5 SP) currently tested, i.e. single-blind. This is possible since the investigator will place the SP on the abutment without showing the subject.

7.2.7 Post-investigation Medical Care

After the investigation a subject will continue to use the SP currently prescribed to him/her.

7.3 Performance Evaluations and Procedures

7.3.1 Eligibility Evaluations and Procedures

Demographics

The following demographic data will be recorded at Screening and Baseline:

- Age collected as date of birth (month and year)
- Gender

Hearing history

During Screening and Baseline a number of baseline characteristics will be recorded:

- Type of hearing loss
- Etiology of hearing loss: (chronic) infection, tumor, trauma, malformation, otosclerosis, other
- Current hearing aid
- Treatment ear

Audiogram

Unaided audiometric threshold measures (including both air- and bone conduction thresholds) should demonstrate whether the subject has a conductive or mild to moderate mixed hearing loss and meets the audiological inclusion criteria.

An existing audiogram may be used as long as it has been completed during the last twelve months and contains all the required relevant frequencies. Frequencies required for air and bone conduction thresholds are 250, 500, 750, 1000, 1500, 2000, 3000, 4000, 6000 and 8000Hz.

If an audiogram is older than 12 months or does not contain the required frequencies, a new audiogram shall be performed at Screening/Baseline. Frequencies required for air and bone conduction thresholds are 250, 500, 750, 1000, 1500, 2000, 3000, 4000, 6000 and 8000Hz. Contralateral masking should be used if needed. The site staff shall always measure both the unmasked thresholds, as well as and the masked thresholds, if applicable.

7.3.2 Post-Enrolment Evaluations and Procedures

[figure not shown]
7.3.3 Adaptive Speech recognition in noise (Matrix test)

The purpose of this test is to establish the test subject's ability to recognise speech in the presence of background noise. The adaptive speech test in noise shall be conducted using validated lists of phonetically balanced sentences, with speech presented in sound-field from the front (0 degrees azimuth) and noise will also be presented from the front (figure 4). The noise shall be kept constant at 65 dB SPL, and the speech shall be adapted stepwise according to the software used to establish the speech-to-noise ratio (SNR) providing a 50% level of understanding.

Software and speech material to be used is the Matrix test in language specific versions as applicable.

The test shall be performed with the non-test ear blocked (in case of normal or near-normal hearing or a large asymmetry with the non-test ear having significantly better hearing thresholds).

The speakers should be at the height of the test subjects head and more than 1 metre away from the test subject. There should preferably be more than 1 metre of free space around the test subject in all directions. This is in accordance with the current standard.

FRONT

Figure 5: Speech in noise speaker position

At Visit 1 and 2, the speech in noise test will be performed for the aided situation with Baha 6 Max SP or Baha 5 SP depending on the randomisation order.

At visit 3 the test will be performed unaided.

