9 STATISTICAL CONSIDERATIONS

9.1 General Statistical Considerations

The investigation will have two primary analyses, one regarding Adaptive speech in noise between Baha 6 Max SP and unaided hearing ($\alpha = 0.005$) and one regarding preference between Baha 6 Max SP and Baha 5 SP ($\alpha = 0.045$). These endpoints will be evaluated using the decision rules of the Holm's test. (Ref NEJM2). With these procedures we will have a total type I error <0.05 .

For the comparison between the Baha 6 Max SP and unaided the design don't take care of period effect so the statistical analyses will be paired. For the comparison between Baha 6 Max SP and Baha 5 SP a cross over design was applied and the statistical analyses will be adjusted for period effect.

The main results for all outcome variables are the estimate of mean differences with 95% confidence interval (CI) with a descriptive p-value. The p-value will only have a confirmatory value for the two primary analyses.

For comparison between the Baha 6 Max SP and unaided Fisher's non-parametric permutation test for paired observations will be used for continuous variables and Sign test for dichotomous variables and ordered categorical variables.

For the comparison between Baha 6 Max SP and Baha 5 SP the following period adjusted analysis should be performed for continuous variables: For each subject take the difference between the measurement in second period and the measurement in first period. Then analyse these differences between the subjects randomised to Baha 6 Max SP in the first period and the subjects randomised to Baha 5 SP in the first period with Fisher's two-sided non-parametric permutation test. The Fisher's permutation test is preferable because it is non-parametric and gives consistent 95% CI.

For the comparison between Baha 6 Max SP and Baha 5 SP the following period adjusted analysis should be performed for dichotomous and ordered categorical variables: For each subject take the difference as, improved no change and worsened, between the measurement in second period and the measurement in first period. Then analyse these ordered categorical differences between the subjects randomised to Baha 6 Max SP in the first period and the subjects randomised to Baha 5 SP in the first period with Mantel-Haenszel chi-square test.

For comparison of preference of device between Baha 6 Max SP and Baha 5 SP the Sign test will be used.

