The distribution of continuous variables will be given as mean, standard deviation, median, Q1, Q3, minimum and maximum and of categorical variables as numbers and percentages.

If a subject completes the cross over part but not the final visit, he will be included in the comparison between Baha 6 Max SP and Baha 5 SP but not in the comparison Baha 6 Max SP vs unaided in FAS.

The investigation will be completed when there are as many available subjects that are needed in the primary analyses.

The main analyses will be on the full analysis set (FAS) and complementary analyses on the Per protocol population. No imputation of missing data will be performed.

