9.4 Sample Size Determination

First primary analysis: Baha 6 Max SP vs unaided regard Adaptive speech in noise

Assuming an individual mean difference (aided Baha 6 Max SP minus unaided) in speech recognition in noise of 16 dB SNR with a standard deviation (SD) of 12.5 (Busch et al, 2015), a total sample of 15 eligible subjects are required to provide 90% power to reject the null hypothesis for the statistical test for the primary objective (change in dB SNR) using a two sided, alpha 0.005, with Two-sided Fisher's non-parametric permutation test for paired observations. As this is an internal Cochlear investigation, patients will be recruited until the number of required patients are obtained. Hence, no dropouts are expected (8).

Second primary analysis: Baha 6 Max SP vs Baha 5 SP regarding preference of device.

Assuming that 86% prefer Baha 6 Max SP, then 16 subjects are needed for 80% power with two-sided Sign test on significance level 0.045.

In order to satisfy both sample sizes for the primary analyses 16 subjects will be randomised into the investigation.

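### Unaided hearing is always tested at Visit 3 and Baha 6 Max never is, so the first primary comparison carries any session effect, and pairing does not remove it

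*Protocol*

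**What the plan says.** Protocol 9.4 names the comparison: "First primary analysis: Baha 6 Max SP vs unaided regard Adaptive speech in noise". Sections 9.3.1 and 9.6 test it with a paired permutation test at the 0.005 level and report a mean difference with a 99.5% confidence interval.

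Section 7.3.3 places the aided Matrix test at Visits 1 and 2, with the randomisation deciding which processor comes first, and then states: "At visit 3 the test will be performed unaided". Sections 7.3.4 and 7.3.5 give the same order for sound-field thresholds and speech in quiet, and the section 3 schedule agrees. Sections 7.1 and 7.2.6 show that only the order of the two processors is randomised.

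Section 9.1 recognises the consequence and settles on a paired analysis, in a sentence that begins "For the comparison between the Baha 6 Max SP and unaided the design don't take care of period effect so the statistical analyses will be". The same section plans a period adjustment for Baha 6 Max versus Baha 5. It plans no sensitivity analysis for test order in the unaided comparison, and the protocol gives no reason for testing unaided last.

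**The concern.** Each subject takes the same test battery three times. If scores move between sessions for any reason other than the device (familiarity with the sentence material, tiredness, motivation), the movement enters the Baha 6 Max minus unaided difference in full, because the two conditions never share a session position. Pairing within subject does not help, since a shift common to all subjects is still there after subtraction.

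Section 7.1.1 gives this comparison as the one intended to support regulatory approval. What is at stake is whether the reported dB benefit and its interval describe the device alone or the device plus an unknown session effect. Speech in quiet, a secondary comparison with unaided, has the same layout.

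**Working it through.** **1. Layout.** With 1:1 allocation of 16 subjects:

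| Sequence | Subjects | Visit 1 | Visit 2 | Visit 3 |
|---|---|---|---|---|
| A | about 8 | Baha 6 Max | Baha 5 | unaided |
| B | about 8 | Baha 5 | Baha 6 Max | unaided |

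**2. What the paired difference estimates.** Let τ be the true benefit, scored so that positive favours the device, and let s1, s2, s3 be additive session effects on the same scale.
- Sequence A: τ + s1 − s3
- Sequence B: τ + s2 − s3
- Average: τ + (s1 + s2)/2 − s3

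Comparing the sequences gives s1 − s2, a Visit 1 to Visit 2 trend. No contrast separates s3 from τ, because s3 occurs only with the unaided condition. Baha 5 data do not help, since Baha 5 is never tested at Visit 3 either. The mean session is 1.5 for Baha 6 Max, (8×1 + 8×2)/16, against 3 for unaided. A steady gain of g dB per session would therefore bias the benefit by 1.5g.

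**3. The plan's own sample size.** Section 9.4 supplies the inputs. The effect is stated as "Assuming an individual mean difference (aided Baha 6 Max SP minus unaided) in speech recognition in noise of 16 dB SNR"; the SD of that difference is 12.5 dB; the test level is given as "using a two sided, alpha 0.005"; and the resulting size reads "a total sample of 15 eligible subjects are required to provide 90% power". Paired-t power from the noncentral t has noncentrality δ√n/SD and n − 1 degrees of freedom.
- n = 14: 89.2%
- n = 15: 92.4%, the smallest n reaching 90%
- n = 16: noncentrality 16/(12.5/4) = 5.12, power 94.7%

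A simulated exact sign-flip permutation test on normal differences gives 88.5% at n = 14 and 92.3% at n = 15. The stated 15 reproduces.

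**4. Session effect favouring unaided.** The documents give no size, so 0 to 3 dB is assumed. Replace δ = 16 by 16 minus the shift:

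| Assumed shift (dB) | Power, n = 16 | Power, n = 15 |
|---|---|---|
| 0 | 94.7% | 92.4% |
| 1 | 91.1% | 87.9% |
| 2 | 85.8% | 81.9% |
| 3 | 78.8% | 74.2% |

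**5. Error rate.** With no true difference, n = 16 and SD 12.5, a shift in either direction takes the two-sided rejection rate from 0.005 to 0.007 (1 dB), 0.013 (2 dB) or 0.025 (3 dB). The direction that matters for a false claim of benefit is a shift against unaided at Visit 3.

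**6. Scale.** Significance at n = 16 needs an observed mean difference of about 10.3 dB (t quantile × 12.5/4). This is also the half-width of the 99.5% interval at that SD. A 3 dB shift is 3/16 = 19% of the planned effect and 3/10.3 = 29% of that half-width.

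**The case against.** The strongest reply is that the limitation is disclosed and small in consequence. Section 9.1 states it openly. Practice, the most obvious mechanism, would favour unaided and make the superiority test conservative. In the other direction, a few dB falls far short of the 10.3 dB needed for significance. All of that stands, and it limits the severity. Disclosure does not correct the estimate, however, and the response given in section 9.1 does not address the problem it names.

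A second reply is that unaided tests placed inside the crossover visits could disturb the balanced Baha 6 Max versus Baha 5 comparison. That would be a fair criticism of always attaching them to the Baha 6 Max visit. It is met if the unaided visit is randomised independently of device order.

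A reader might also infer more than the documents support:
- *That the title is wrong.* Randomised test order is true of the two processors, and nothing claims that the unaided slot is randomised.
- *That Visit 3 is long and tiring, or run under different conditions.* No visit durations are given, and section 7.5 fixes one sound-insulated room and an unchanged set-up.
- *That practice with speech material biases the thresholds.* Those use warble tones (section 7.3.4). They share the layout but not this mechanism.
- *That a practice run is ruled out.* The text describes none, but the figure in section 7.3.2 is not available.
- *That a missed Visit 3 is part of this problem.* Section 9.1 does drop such subjects from the unaided comparison, but that is a missing-data matter, and device preference is also collected at Visit 3.

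**Conclusion.** The point holds for the protocol's first primary comparison. Condition and session are aliased by design, and neither pairing nor any other analysis of these data can separate them. The direction and size of the session effect are unknown; the 1 to 3 dB range is an assumption. The power and error figures rest on the planning values, a paired-t approximation and an additive shift common to all subjects.

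The main harm is bias, dB for dB, in the estimated benefit and its 99.5% interval. Loss of power is possible: at n = 16, an assumed 2 dB practice gain takes it below the planned 90%. It would be tempting to conclude that a positive superiority result could not be trusted. The figures do not support that: against a planned 16 dB, a small shift is unlikely to change the conclusion.

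One limit on reach: SAP 4.2.1 and 4.2.2 define the first primary hypothesis as responders on Baha 6 Max versus Baha 5, while SAP 4.1 keeps the sample size for the unaided comparison. That conflict is a separate matter and must be resolved on its own.

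**What to change.** In protocol sections 3 and 7.3.3 to 7.3.5:
- Move the unaided tests from Visit 3 to Visit 1 or Visit 2, randomised within each device sequence and independently of device order.
- Randomise whether the unaided or the aided battery comes first within that visit. Two sequences × two visits × two orders gives 8 cells, so 16 subjects fill them with 2 each.
- Give one unscored Matrix practice list before the first scored list.
- Revise the section 9.1 sentence on period effect to describe the new balance.

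Check of the balance over the three scored batteries. Unaided has mean position 1.5 if placed at Visit 1 and 2.5 if at Visit 2, average 2. The first device averages (1.5 + 1)/2 = 1.25 and the second (3 + 2.5)/2 = 2.75. Each processor is first in half the subjects, so each averages (1.25 + 2.75)/2 = 2. All three conditions then share the same mean position, and the crossover comparison stays balanced. The paired sample size of 15 is unchanged under the same assumptions.

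Cost: a protocol amendment, one longer visit per subject (Visit 3 becomes shorter) and a few minutes of practice. The numbers of visits and scored tests do not change.

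If the schedule cannot be changed, state the limitation and both possible directions of bias, and report the paired difference by sequence. That would show a Visit 1 to Visit 2 trend but could not identify the Visit 3 effect.
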